CLINICAL TRIAL PROTOCOL

COMPOUND: Dupilumab/SAR231893

**Open-label, interventional, cohort study to evaluate long-term safety of dupilumab
in patients with moderate to severe asthma who completed the
TRAVERSE-LTS12551 clinical trial**

STUDY NUMBER: LPS15023

STUDY NAME: LONG-TERM FOLLOW-UP

Version Number:	1	EudraCT	2017-002134-23
		IND Numbers	IND105379
		WHO universal trial number:	U1111-1196-5369
Date:	27-Feb-2018	Total number of pages:	61

Any and all information presented in this document shall be treated as confidential and shall remain the exclusive property of Sanofi (or any of its affiliated companies). The use of such confidential information must be restricted to the recipient for the agreed purpose and must not be disclosed, published or otherwise communicated to any unauthorized persons, for any reason, in any form whatsoever without the prior written consent of Sanofi (or the concerned affiliated company); 'affiliated company' means any corporation, partnership or other entity which at the date of communication or afterwards (i) controls directly or indirectly Sanofi, (ii) is directly or indirectly controlled by Sanofi, with 'control' meaning direct or indirect ownership of more than 50% of the capital stock or the voting rights in such corporation, partnership or other entity

NAMES AND ADDRESSES OF

COORDINATING INVESTIGATOR

Name:
Address:

Tel:
Fax:
E-mail:

MONITORING TEAM'S REPRESENTATIVE

Name:
Address:

Tel:
Fax:
E-mail:

SPONSOR

Company:
Address:

OTHER EMERGENCY TELEPHONE NUMBERS

CLINICAL TRIAL SUMMARY

COMPOUND: Dupixent®	STUDY No.: LPS15023 STUDY NAME: LONG-TERM FOLLOW-UP
TITLE	Open-label, interventional, cohort study to evaluate long-term safety of dupilumab in patients with moderate to severe asthma who completed the TRAVERSE-LTS12551 clinical trial
INVESTIGATOR/TRIAL LOCATION	International
PHASE OF DEVELOPMENT	Phase IIIb
STUDY OBJECTIVE	Primary objective: 
• To describe the long-term safety of dupilumab in the treatment of patients with moderate to severe asthma who completed the previous asthma clinical trial, TRAVERSE-LTS12551.
STUDY DESIGN	Open-label, interventional, outpatient, prospective, multinational, multicenter, noncomparative, single-arm, safety study.
STUDY POPULATION Main selection criteria	Inclusion criteria: 
I 01. Patient with asthma who completed the treatment period in the previous dupilumab asthma clinical study TRAVERSE-LTS12551.I 02. Patient is on background dose of medium or high dose inhaled corticosteroid (ICS), as maintained during study TRAVERSE-LTS12551, in combination with a second controller (and/or oral corticosteroid [OCS] for those patients from the original parent study EFC13691). Patients requiring a third controller medication will be allowed (eg, long-acting β-adrenoceptor agonists [LABA], leukotriene receptor antagonist [LTRA], methylxanthines).I 03. Signed written informed consent. Exclusion criteria: 
E 01. Current smoker or cessation of smoking within 6 months prior to enrollment.E 02. Clinically significant comorbidity/lung disease other than asthma.E 03. Alcohol abuse or drug abuse.E 04. Inability to follow drug administration procedures/noncompliance (eg, due to language problems or psychological disorders).E 05. Patient who have received, in the last 3 months, concomitant prohibited treatment:
• Anti-immunoglobulin (Ig) E therapy (eg, omalizumab);• Biologic therapy.• Systemic immunosuppressants.• Intravenous Ig therapy.• Nonselective β-adrenergic blockers.• Other investigational drugs.• Live/attenuated vaccines.

	
E 06. Patient who develops: a new medical condition or a change in status of an established medical condition; a laboratory abnormality, or requires a new treatment or medication prior to enrollment, which (per Investigator's medical judgment) would adversely affect the participation in this study or would require permanent investigational medicinal product (IMP) discontinuation.
 
E 07. Pregnant or breastfeeding women.
 
E 08. Women of child-bearing potential (WOCBP, following menarche and until becoming post menopausal unless permanently sterile) who:
 
• Do not have a confirmed negative urine test at enrollment.• Who are not protected by one of the following acceptable forms of effective contraception during the study (from Visit 1 to End-of-treatment [EOT]/End-of-study [EOS]):
- Established use of oral, injected, implanted, or inserted hormonal contraceptive.- Intrauterine device with copper or intrauterine system with progestogen.- Contraceptive barrier (condom, diaphragm, or cervical/vault caps) used with spermicide (foam, gel, film, cream, or suppository).- Female sterilization (eg, tubal occlusion, hysterectomy, or bilateral salpingectomy).- Male sterilization with post vasectomy documentation of the absence of sperm in the ejaculate; for female patients in the study, the vasectomized male partner should be the sole partner of that patient.- True abstinence; periodic abstinence (eg, calendar, ovulation, symptothermal, post ovulation methods) is not an acceptable method of contraception.- Menopausal women (defined as at least 12 consecutive months without menses) are not required to use additional contraception.
	
E 09. Diagnosed active parasitic infection; suspected or high risk of parasitic infection, unless clinical and (if necessary) laboratory assessments have ruled out active infection before the enrollment.

	
E 10. Patients with active autoimmune disease (eg, rheumatoid arthritis, inflammatory bowel disease, primary biliary cirrhosis, systemic lupus erythematosus, multiple sclerosis) or patients who, as per Investigator's medical judgment, are suspected of having high risk for developing autoimmune disease.

	
E 11. Patients who experienced any systemic hypersensitivity reactions to the IMP in the previous dupilumab asthma study TRAVERSE-LTS12551, which, in the opinion of the Investigator, could indicate that continued treatment with dupilumab may present an unreasonable risk for the patient.

	
E 12. Blood eosinophils >1500 cells/mm³ at the latest available test.

	E 13. History of malignancy within 5 years before enrollment except completely treated in situ carcinoma of the cervix, completely treated and resolved nonmetastatic squamous or basal cell carcinoma of the skin.
Total expected number of patients	750
STUDY TREATMENTS	
Investigational medicinal product	Dupilumab
Formulation	Dupilumab 300 mg prefilled syringes of 150 mg/mL (2.25 mL total volume) to deliver 300 mg in the extractable 2 mL volume.
Route of administration	Subcutaneous (SC).
Dose regimen	300 mg SC every 2 weeks (q2w) with a 600 mg loading dose on Visit 1 (Start-of-treatment Visit) for patients who discontinued treatment for \geq 6 weeks after study TRAVERSE-LTS12551.
Noninvestigational medicinal products	
Asthma background controller therapy: Inhaled corticosteroid, in combination with a second controller. Patients requiring a third controller medication will be allowed (eg, LABA, LTRA, methylxanthines); OCS will be allowed only for those patients from original parent study EFC13691.
 
Asthma reliever medication: Patients may receive salbutamol/albuterol hydrofluoroalkane pressurized metered dose inhalers (MDI) or levosalbutamol/levalbuterol hydrofluoroalkane pressurized MDI as reliever medication (as needed) during the study. Nebulizer solutions with either albuterol/salbutamol or levalbuterol/levosalbutamol may be used as an alternative delivery method.

Post trial access to study medication	By continuing to describe long-term safety, this study provides post trial access to study medication for patients from TRAVERSE-LTS12551.
ENDPOINTS	
Primary safety endpoint: Incidence rates, defined as percentage of patients with treatment-emergent adverse events (TEAEs) and event rates per 100 patient-years.
 
Secondary endpoints:
 
 Incidence rates and event rates per 100 patient-years for adverse events of special interest (AESIs) over the study. Incidence rates for serious adverse events (SAEs)/death over the study. Incidence rates for adverse events (AEs) leading to study discontinuation over the study.
ASSESSMENT SCHEDULE	
Visit schedule: On-site visits every 12 weeks throughout the study, for a maximum of 12 post baseline visits. The Start-of-treatment (Visit 1) may be performed on the same day as the TRAVERSE-LTS12551 EOT Visit.
 
Early termination: Patients who prematurely and permanently discontinue IMP administration should have the EOT/EOS Visit (Visit 13) performed. Women of child-bearing potential discontinuing treatment will be advised to avoid pregnancy for at least 12 weeks following the last IMP dose.

STATISTICAL CONSIDERATIONS	
Sample size determination: Qualifying patients completing the treatment period of study TRAVERSE-LTS12551 will be offered to continue in this study.
 
Primary analysis population: Safety: All patients receiving at least one dose of study medication during this study.
 
Primary/key analysis: All TEAEs, AESIs, SAEs, and AEs leading to treatment discontinuation will be summarized.

DURATION OF STUDY PERIOD (per patient)	Until dupilumab approval for use in asthma and market availability to the patient, or for a maximum of 144 weeks (ie, about 3 years) after the Start-of-treatment (Visit 1), whichever comes first.

1 FLOW CHARTS

1.1 STUDY FLOW CHART

Study periods	Start-of-Treatment	Treatment Period (144 weeks)	End-of-Treatment / End-of-Study
Week (W)	W0	W12-W132 (Visit every 12 weeks)	W144
VISIT	V1 ^a	V2-V12 ^b	V13 ^c
Enrollment			
Informed consent	X		
Patient demography	X		
Eligibility criteria	X		
Treatment			
Contact IRT	X	X	X
IMP dispensation/administration ^d	X	X	
IMP accountability	X	X	X
Injection training/technique observation ^e	X	X	
Dispense home-dosing diary ^f	X	X	
Safety			
Clinical laboratory ^g	X ^h	X	X
Adverse event reporting	X	X	X
Symptom-driven physical examination and vital signs	X	X	X
Concomitant medications	X	X	X

AE = adverse events; eCRF = electronic case report form; EOS = end-of-study; EOT = end-of-treatment; IMP = investigational medicinal product; IRT = interactive response technology; q2w = every 2 weeks; V = (study) visit; W = (study) week; WOCBP = women of child-bearing potential.

a After completing the EOT Visit (V17) in study TRAVERSE-LTS12551, eligible patients should perform Start-of-treatment (V1) in LPS15023.

Additional on-site IMP administration visits may be scheduled at the Investigator's discretion for patients who experience hypersensitivity reactions upon retreatment at this visit, or for patients with long off-treatment interval after the completion of study TRAVERSE-LTS12551.

b Visit window is ± 7 days with respect to V1, ensuring at least an 11-day interval between 2 consecutive dupilumab administrations.

c Patients who prematurely and/or permanently discontinue treatment will be scheduled for the EOT Visit, and the EOS Visit will be scheduled for 12 weeks later for follow-up on AEs.

d Dispensation of IMP at every visit (except at EOT/EOS). Administration of 300 mg q2w. Loading dose of 600 mg at V1 for patients who discontinued treatment for ≥ 6 weeks after TRAVERSE-LTS12551. For administrations coinciding with site visits, patients will be monitored at the study site for a minimum of 30 minutes after injections.

e The Investigator or delegate must train the patient (or parent/caregiver[s]) at V1, if starting self-administration, on the preparation and injection of IMP, and review the patient's administration technique at subsequent visits if needed.

f The home-dosing diary should be dispensed at the time of injection training/technique observation.

g Local laboratory tests: Hematology (blood count: erythrocytes, hemoglobin, hematocrit, leukocytes with differential blood count [neutrophils, lymphocytes, monocytes, eosinophils, and basophils], and platelets), and pregnancy test (urine or blood, for WOCBP only). Only clinically significant values will be captured in the eCRF.

h Only for patients who do not roll-over into the study within 4 weeks of EOT or EOS Visit for study TRAVERSE-LTS12551 (see [Section 10.1.1](#)).

3 LIST OF ABBREVIATIONS

AEs:	adverse events
AESIs:	adverse events of special interest
CYP:	cytochrome P450
DRF:	discrepancy resolution form
eCRF:	electronic case report form
EOS:	end-of-study
EOT:	end-of-treatment
GCP:	good clinical practice
HLGT:	high level group term
IB:	investigator's brochure
ICF:	informed consent form
ICH:	International Council for Harmonisation
ICS:	inhaled corticosteroids
IEC:	Independent Ethics Committee
Ig:	immunoglobulin
IL:	interleukin
IL-4R α :	interleukin-4 receptor alpha
IMP:	investigational medicinal product
IRB:	Institutional Review Board
IRT:	interactive response technology
LABA:	long-acting β -adrenoceptor agonists
LTRA:	leukotriene receptor antagonist
MDI:	metered dose inhalers
NIMP:	noninvestigational medicinal products
OCS:	oral corticosteroids
PT:	preferred term
q2w:	every 2 weeks
SAEs:	serious adverse events
SC:	subcutaneously
SD:	standard deviation
SOC:	system organ class
TB:	tuberculosis
TEAEs:	treatment-emergent adverse events
Th2:	Type 2 T-helper cell
WOCBP:	women of child-bearing potential

4 INTRODUCTION AND RATIONALE

4.1 INTRODUCTION

Asthma is a chronic inflammatory disease of the airways characterized by airway hyper-responsiveness, acute and chronic bronchoconstriction, airway edema, and mucus plugging.

The inflammatory component of asthma involves many cell types, including mast cells, eosinophils, T-lymphocytes, neutrophils, epithelial cells, and their biological products. For most asthma patients, a regimen of controller therapy and reliever therapy provides adequate long-term control. However, it is estimated that 5% to 10% of asthma patients have symptomatic disease despite maximum recommended treatment with combinations of anti-inflammatory and bronchodilator drugs (1).

The poor response of some patients with asthma may reflect the number of cellular and molecular mechanisms operative in asthma. There is increasing interest in distinct phenotypes because targeted therapy is more likely to be successful in patients with similar underlying pathobiologic features (2). Recent therapeutic approaches in asthma have been focused on trying to control the Type 2 T-helper cell (Th2) response. Up-regulation of interleukin(IL)-4 and IL-13 has been implicated as an important inflammatory component of asthma disease progression.

Dupilumab, a fully human monoclonal antibody that binds specifically to the shared interleukin-4 receptor alpha (IL-4R α) subunit of the IL-4 and IL-13 receptor complexes, is under development as a potential novel treatment for asthma. Dupilumab inhibits IL-4 signaling via the Type I receptor, and both IL-4 and IL-13 signaling through the Type II receptor. Dupilumab belongs to the pharmacological class of immunomodulators, IL inhibitors.

For complete information regarding the preclinical and clinical evaluation of dupilumab to date, including ongoing studies, see the current version of the Investigator's Brochure (IB).

4.2 RATIONALE

From an efficacy perspective, the dosing regimen of 300 mg every 2 weeks (q2w), added to a medium-to-high dose inhaled corticosteroids (ICS) + long-acting β -adrenoceptor agonists (LABA) in adult patients with uncontrolled persistent asthma, showed a clinically meaningful and highly statistically significant reduction versus placebo in the relative risk of severe exacerbations, improvement in lung function ie, forced expiratory volume and asthma symptoms (Asthma Control Questionnaire 5-question Version) (3).

From a safety perspective, dupilumab 300 mg q2w demonstrated an acceptable safety profile and was well tolerated in pivotal trials for asthma and other indications (3, 4), as well as in the long-term safety study TRAVERSE-LTS12551 at the time of the interim analysis at median treatment duration of 51 weeks (data collection cut-off on 31 January 2016).

Overall, approximately 7004 subjects had been enrolled into the dupilumab development program as of 31 May 2017: 222 healthy volunteers, 3392 patients with atopic dermatitis (AD), 3009 patients with asthma, 334 patients with nasal polyposis, and 47 patients with eosinophilic esophagitis. The estimated total number of subjects exposed to dupilumab in clinical studies was 6250 (3286 in AD, 2546 in asthma, 193 in nasal polyposis and 23 in eosinophilic esophagitis, and 202 in healthy volunteer studies).

Study TRAVERSE-LTS12551 (the “parent” study) was designed as an open-label extension study to evaluate the long-term safety and tolerability of dupilumab in patients with asthma who participated in previous dupilumab studies (DRI12544, PDY14192, EFC13579, and EFC13691).

The current LPS15023 study will provide further long-term clinical safety data (adverse events [AEs]/serious adverse events [SAEs] reporting) on dupilumab and extended dupilumab treatment to patients who continue to benefit from treatment. Therefore, a simplified study design is adopted, focusing on long-term clinical safety and late-onset events, while removing the burden of efficacy and patient reported outcome assessments. Safety monitoring will include continued focus on AEs, SAEs, and adverse events of special interest (AESIs, see [Section 10.4.1.3](#)).

5 STUDY OBJECTIVES

5.1 PRIMARY

The primary objective of this study is to describe the long-term safety of dupilumab in the treatment of patients with moderate to severe asthma who completed the previous asthma clinical trial, TRAVERSE-LTS12551.

6 STUDY DESIGN

6.1 DESCRIPTION OF THE STUDY

The LPS15023 study is a Phase IIIb, open-label, interventional, outpatient, prospective, multinational, multicenter, noncomparative, single-arm, safety study in patients with moderate to severe asthma who completed the parent study, TRAVERSE-LTS12551, from here on referred to as TRAVERSE.

This study will evaluate the long-term safety of dupilumab 300 mg q2w administered subcutaneously (SC) over a maximum of 144 weeks.

6.2 DURATION OF STUDY PARTICIPATION

6.2.1 Duration of study participation for each patient

The LPS15023 study consists of 3 periods:

- Start-of-treatment (Visit 1).
- Treatment period (Visit 2 to Visit 12).
- End-of-treatment (EOT)/End-of-study (EOS) (Visit 13).

Patients who prematurely and/or permanently discontinue treatment will be scheduled for the EOT Visit, and the EOS Visit will be scheduled for 12 weeks later for follow-up on AEs.

After completing the treatment period in TRAVERSE, eligible patients who have signed the informed consent form (ICF) should perform the assessments of the Start-of-treatment Visit (Visit 1). Patients will receive treatment until dupilumab approval for use in asthma and market availability to patients, or for a maximum of 144 weeks (ie, about 3 years) after the Start-of-treatment (Visit 1), whichever comes first.

6.2.2 Determination of end of clinical trial (all patients)

The end of clinical trial is defined as the “last patient last visit” planned in the protocol, ie, the EOT/EOS Visit (Visit 13). The Sponsor reserves the right to discontinue the study at any time.

6.3 INTERIM ANALYSIS

Interim analyses of data may be conducted to support regulatory submissions or publication activities.

6.4 STUDY COMMITTEES

Not applicable.

7 SELECTION OF PATIENTS

7.1 INCLUSION CRITERIA

- I 01. Patient with asthma who completed the treatment period in TRAVERSE.
- I 02. Patient is on background dose of medium or high dose ICS, as maintained during TRAVERSE, in combination with a second controller (and/or oral corticosteroids [OCS] for those patients from the original parent study EFC13691). Patients requiring a third controller medication will be allowed (eg, LABA, leukotriene receptor antagonist [LTRA], methylxanthines).
- I 03. Signed informed consent.

7.2 EXCLUSION CRITERIA

Patients who have met all inclusion criteria listed in [Section 7.1](#) will be screened for the following exclusion criteria:

- E 01. Current smoker or cessation of smoking within 6 months prior to enrollment.
- E 02. Clinically significant comorbidity/lung disease other than asthma.
- E 03. Alcohol abuse or drug abuse.
- E 04. Inability to follow drug administration procedures/noncompliance (eg, due to language problems or psychological disorders).
- E 05. Patient who have received, in the last 3 months, concomitant prohibited treatment:
 - Anti-immunoglobulin (Ig) E therapy (eg, omalizumab).
 - Biologic therapy.
 - Systemic immunosuppressants.
 - Intravenous Ig therapy.
 - Nonselective β -adrenergic blockers.
 - Other investigational drugs.
 - Live/attenuated vaccines (see [Appendix A](#)).
- E 06. Patient who develops: a new medical condition or a change in status of an established medical condition; a laboratory abnormality, or requires a new treatment or medication prior to enrollment, which (per Investigator's medical judgment) would adversely affect the participation in this study or would require permanent investigational medicinal product (IMP) discontinuation.

E 07. Pregnant or breastfeeding women.

E 08. Women of child-bearing potential (WOCBP, following menarche and until becoming post menopausal unless permanently sterile) who:

- Do not have a confirmed negative urine test at enrollment.
- Who are not protected by one of the following acceptable forms of effective contraception during the study (from Visit 1 to EOT/EOS):
 - Established use of oral, injected, implanted, or inserted hormonal contraceptive.
 - Intrauterine device with copper or intrauterine system with progestogen.
 - Contraceptive barrier (condom, diaphragm, or cervical/vault caps) used with spermicide (foam, gel, film, cream, or suppository).
 - Female sterilization (eg, tubal occlusion, hysterectomy, or bilateral salpingectomy).
 - Male sterilization with post vasectomy documentation of the absence of sperm in the ejaculate; for female patients in the study, the vasectomized male partner should be the sole partner of that patient.
 - True abstinence; periodic abstinence (eg, calendar, ovulation, symptothermal, post ovulation methods) is not an acceptable method of contraception.
 - Menopausal women (defined as at least 12 consecutive months without menses) are not required to use additional contraception.

E 09. Diagnosed active parasitic infection; suspected or high risk of parasitic infection, unless clinical and (if necessary) laboratory assessments have ruled out active infection before the enrollment.

E 10. Patients with active autoimmune disease (eg, rheumatoid arthritis, inflammatory bowel disease, primary biliary cirrhosis, systemic lupus erythematosus, multiple sclerosis) or patients who, as per Investigator's medical judgment, are suspected of having high risk for developing autoimmune disease.

E 11. Patients who experienced any systemic hypersensitivity reactions to the IMP in TRAVERSE, which, in the opinion of the Investigator, could indicate that continued treatment with dupilumab may present an unreasonable risk for the patient.

E 12. Blood eosinophils >1500 cells/mm³ at the latest available test.

E 13. History of malignancy within 5 years before enrollment except completely treated in situ carcinoma of the cervix, completely treated and resolved nonmetastatic squamous or basal cell carcinoma of the skin.

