10.1.1 Visit 1 (Start-of-treatment, Week 0)

There is no time limit between the TRAVERSE EOT Visit and the evaluation for eligibility to participate in this study.

Ideally, patients should be evaluated for eligibility to participate in this study as soon as they complete the TRAVERSE EOT Visit. The Start-of-treatment (Visit 1) for this study may be performed on the same day as the TRAVERSE EOT Visit. If this is not possible or if the patient completed participation in TRAVERSE prior to the opening of enrollment in this study, and more than 4 weeks have elapsed between TRAVERSE EOT Visit date and the LPS15023 Start-of-treatment (Visit 1) date, the following additional assessments will be required:

- Collect blood samples for hematology: Blood count (erythrocytes, hemoglobin, hematocrit, and leukocytes), differential blood count (neutrophils, lymphocytes, monocytes, eosinophils, and basophils), and platelets.
- For **WOCBP only**, blood or urine pregnancy test.

Following a discussion of participation in the clinical trial, the written informed consent (and assent in case of adolescents) form must be signed and dated before the following activities are performed:

- Review inclusion and exclusion criteria to assess eligibility.
- If the patient meets all inclusion and does not meet any exclusion criteria, contact IRT to register the visit, confirm the patient's number and receive the first treatment kits' numbers assignment.

- Confirm and update (if required) previously collected patient's demographic information, asthma history (including allergy history and smoking habits), and other medical and surgical history (including significant prior and concurrent illnesses).
- Symptom-driven physical examination and vital signs should be performed in patients presenting with signs or symptoms.
- Commence AE reporting from the time of the signature of the informed consent for participation in LPS15023.
- Record study IMP/noninvestigational medicinal products (NIMP) and all other concomitant medication use with start date/dose in the eCRF.
- Instruct the patient to continue the background ICS/LABA or ICS and controller therapy stabilized during TRAVERSE.
- Dispense and administer IMP (see [Section 8.1.3](#)):

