- a After completing the EOT Visit (V17) in study TRAVERSE-LTS12551, eligible patients should perform Start-of-treatment (V1) in LPS15023. Additional on-site IMP administration visits may be scheduled at the Investigator's discretion for patients who experience hypersensitivity reactions upon retreatment at this visit, or for patients with long off-treatment interval after the completion of study TRAVERSE-LTS12551.
- b Visit window is ± 7 days with respect to V1, ensuring at least an 11-day interval between 2 consecutive dupilumab administrations.
- c Patients who prematurely and/or permanently discontinue treatment will be scheduled for the EOT Visit, and the EOS Visit will be scheduled for 12 weeks later for follow-up on AEs.
- d Dispensation of IMP at every visit (except at EOT/EOS). Administration of 300 mg q2w. Loading dose of 600 mg at V1 for patients who discontinued treatment for ≥ 6 weeks after TRAVERSE-LTS12551. For administrations coinciding with site visits, patients will be monitored at the study site for a minimum of 30 minutes after injections.
- e The Investigator or delegate must train the patient (or parent/caregiver[s]) at V1, if starting self-administration, on the preparation and injection of IMP, and review the patient's administration technique at subsequent visits if needed.
- f The home-dosing diary should be dispensed at the time of injection training/technique observation.

Statistical Analysis Plan 15-Mar-2021
LPS15023 - Dupilumab Version number: 2.0
g Local laboratory tests: Hematology (blood count: erythrocytes, hemoglobin, hematocrit, leukocytes with differential blood count [neutrophils, lymphocytes, monocytes, eosinophils, and basophils], and platelets), and pregnancy test (urine or blood, for WOCBP only). Only clinically significant values will be captured in the eCRF.
h Only for patients who do not roll-over into the study within 4 weeks of EOT or EOS Visit for study TRAVERSE-LTS12551 (see protocol [Section 10.1.1](#)).

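### E 08 requires a negative pregnancy test at enrollment for every WOCBP, but the Visit 1 schedule orders one only when rollover is not within 4 weeks of TRAVERSE

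*Protocol*

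**What the plan says.** **Criterion.** Protocol 7.2, E 08, repeated in the synopsis, excludes WOCBP who "Do not have a confirmed negative urine test at enrollment". It makes no exception by rollover time. Section 8.4 defines enrollment as the assignment of a kit number by the IRT, places it at Visit 1, and stresses that every criterion be confirmed beforehand.

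**Schedule.** Protocol 10.1.1 lists hematology and, for WOCBP, a blood or urine pregnancy test as extra Visit 1 assessments. They are required when "more than 4 weeks have elapsed between TRAVERSE EOT Visit date and the LPS15023 Start-of-treatment (Visit 1) date". In the flow chart (1.1), footnote g places the pregnancy test within the clinical laboratory row, and footnote h restricts the Visit 1 cell of that row: "Only for patients who do not roll-over into the study within 4 weeks of EOT or EOS Visit". SAP 1.4 carries the same footnote: "Only for patients who do not roll-over into the study within 4 weeks of EOT or EOS Visit for study TRAVERSE-LTS12551".

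**Eligibility check.** Section 10.1.1 also gives two instructions for every patient: "Review inclusion and exclusion criteria to assess eligibility", and then "If the patient meets all inclusion and does not meet any exclusion criteria, contact IRT to register the visit".

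**The concern.** For a WOCBP who rolls over within 4 weeks, the criterion demands a test that the list of Visit 1 procedures leaves out. This is not an unusual route. Section 10.1.1 prefers it ("Ideally, patients should be evaluated for eligibility to participate in this study as soon as they complete the TRAVERSE EOT Visit") and allows Visit 1 on the TRAVERSE EOT day.

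Sites could act differently. One working from the flow chart might enroll without a test, which would be an eligibility deviation under E 08. Another might rely on a recent TRAVERSE result, with nothing to say whether that is acceptable. The clinical stake is exposure of an unrecognized pregnancy. E 07 excludes pregnant women, and section 10.3 makes pregnancy a reason to stop dupilumab permanently in every case.

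**Working it through.** The plan gives no figure to reproduce. The check compares texts and then does calendar arithmetic.

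**Texts side by side**

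| Rollover after TRAVERSE EOT | E 08 with 8.4 | 10.1.1 and footnote h |
|---|---|---|
| Same day | Negative test needed at enrollment | No Visit 1 test ordered |
| 1 to 28 days | Negative test needed at enrollment | No Visit 1 test ordered |
| More than 4 weeks (counted from EOT) | Negative test needed at enrollment | 10.1.1 orders a blood or urine test |

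The first two rows conflict unless a TRAVERSE result counts for E 08. No sentence says that it does. The authors did accept an earlier result elsewhere: E 12 judges eosinophils "at the latest available test". E 08 has no such wording.

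**First scheduled test if none is done at entry**

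- Visit 2 is at Week 12: 12 × 7 = day 84, counting Visit 1 as day 0.
- The window is ±7 days (flow chart footnote b): 84 − 7 = 77 and 84 + 7 = 91, so day 77 to 91.

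**Planned doses before that test**

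- Dosing is every 14 ± 3 days, with doses at least 11 days apart (8.1.3).
- Nominal doses at Weeks 0, 2, 4, 6, 8 and 10 fall on days 0, 14, 28, 42, 56 and 70. That is six doses before Week 12.
- The count moves with the windows. On strictly nominal dosing the seventh dose falls on day 84, so a Visit 2 on day 85 to 91 follows seven doses. At the shortest interval, doses on days 0, 11, 22, 33, 44, 55 and 66 give seven before day 77.

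**Interval between scheduled tests, assuming a test at TRAVERSE EOT**

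The documents do not state that such a test is done. With a gap of 0 to 28 days before Visit 1:

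- shortest: 0 + 77 = 77 days (11 weeks)
- longest: 28 + 91 = 119 days (17 weeks)

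**The case against.** The strongest defence is that the texts can be read together. E 08 sets a status the woman must have. Section 10.1.1 does not forbid a Visit 1 test or waive E 08; it adds assessments once 4 weeks have passed. That suggests the TRAVERSE EOT assessments are meant to serve for prompt rollovers, with 4 weeks as the limit on their age. This may well be the intention, and for same-day rollover it would be reasonable. But it is nowhere stated, it assumes a TRAVERSE test that these documents do not show, and a result from 1 to 28 days earlier fits poorly with a test at enrollment.

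The second defence is that a check already stands before dosing. Under 8.4 and 10.1.1 a compliant site cannot enroll a WOCBP who fails E 08. This stands and limits the harm, but it leaves the criterion and the schedule in disagreement.

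The defence can add that WOCBP must use effective contraception and are tested every 12 weeks, and that SAP 2.1.1 tabulates whether a pregnancy test was performed and its result. The first two reduce the risk. The tabulation would only describe an omission afterwards.

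A reader might infer that the protocol lets prompt-rollover women be treated untested until Week 12. The documents do not support that, because E 08 still binds the site. A reader might also infer an exact dose limit, such as seven doses only when Visit 2 falls on day 88 to 91, or that no loading dose could apply. The first mixes nominal days for the early doses with a window for the seventh. The second is not established: the 6-week loading rule runs from stopping treatment, the 4-week rule from EOT (or from EOT or EOS in footnote h), and the time from the last TRAVERSE dose to those visits is not given.

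**Conclusion.** The inconsistency is real and should be corrected. The conclusion rests on the wording of E 08, 8.4, 10.1.1 and footnotes g and h, and on the absence of any rule accepting a TRAVERSE result.

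The exposure consequence is conditional on a site following the flow chart and doing no entry test despite E 08. The delay and dose count above apply only then. Whether TRAVERSE EOT includes a pregnancy test, and how many WOCBP roll over within 4 weeks, cannot be determined from these documents. The matter concerns eligibility and fetal safety; it changes no endpoint or analysis.

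**What to change.** In Protocol 10.1.1, flow chart footnote h and the SAP 1.4 copy, limit the 4-week condition to hematology. Require a local urine or blood pregnancy test for every WOCBP at Visit 1, with a negative result before IRT kit assignment and the first dose. State that a test done the same day at the TRAVERSE EOT visit is accepted.

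Two wording points can be aligned at the same time. E 08 (7.2 and synopsis) should accept urine or blood, as 10.1 and 10.1.1 already do. The 4 weeks should be counted from TRAVERSE EOT throughout, since footnote h now says EOT or EOS.

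An alternative is to let E 08 accept a negative TRAVERSE EOT result within a stated number of days. That would also end the conflict, but it leaves an interval without a test before the first dose and depends on TRAVERSE doing the test.

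The cost of the preferred change is a text amendment and at most one local test per WOCBP at Visit 1, which E 08 on its plain wording already requires. No extra test is needed where a same-day TRAVERSE EOT test exists.
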